## • QUALITY OF LIFE WITH VENOUS INSUFFICIENCY

1) During the past four weeks, have you had any **pain** in your **ankles** or **legs**, and how severe has this pain been?  
Circle the number that applies to you.

No  
pain  
Slight  
pain  
Moderate  
pain  
Considerable  
pain  
Severe  
pain

1  
2  
3  
4  
5

2) During the past four weeks, how much trouble have you experienced at **work** or during your **usual daily activities because of your leg problems?**

Circle the number that applies to you.

No trouble  
Slight trouble  
Moderate trouble  
Considerable trouble  
Severe trouble

1  
2  
3  
4  
5

**3)** During the past four weeks, have you **slept badly** because of your leg problems, and how often?  
Circle the number that applies to you.

Never  
Rarely  
Fairly  
often  
Very  
often  
Every  
night  
1  
2  
3  
4  
5

During the past four weeks, how much **trouble** have you experienced **carrying out the actions and activities** listed below **because of your leg problems?**

For each statement in the table below, indicate how much trouble you have experienced by circling the number chosen.

No trouble  
Slight trouble  
Moderate trouble  
Considerable trouble  
Could not  
do it

**4)** Climbing several flights of stairs

1  
2  
3  
4

**5)** Crouching,

Kneeling down

1  
2  
3  
4  
5

**6)** Walking at a brisk pace

1  
2  
3  
4  
5

**7)** Going out for the evening, going to a wedding, a party, a cocktail party...

1  
2  
3  
4  
5

**8)** Playing a sport, exerting yourself physically

1  
2  
3  
4  
5

Leg problems can also affect your mood. How closely do the following statements correspond to what you have felt during the past four weeks?

For each statement in the table below, circle the number that applies to you.

Not at all

A little

Moderately

A lot

Completely

**9)** I have felt nervous/tense

1  
2  
3  
4  
5

**10)** I have felt I am a burden

1  
2  
3

4

5

**11)** I have felt embarrassed about showing my legs

1

2

3

4

5

**12)** I have become irritated easily

1

2

3

4

5

**13)** I have felt as if I am handicapped

1

2

3

4

5

**14)** I have not felt like going out

1

2

3

4

5

## **Appendix 9. Patient Diary**

Please indicate at what stage you were able to return to work and your normal daily activities (the activities you were able to do prior to your treatment)

**Day I was able to resume my normal activities**

**(please tick one box)**

**Day I returned to work (please tick one box)**

Day of surgery

Day after surgery

2 days after surgery

3 days after surgery

4 days after surgery

5 days after surgery

6 days after surgery

7 days after surgery

8 days after surgery

9 days after surgery

10 days after surgery

>10 days after surgery

•

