### **The Normal Care Pathway,(NCP)**

In the normal care pathway, patients referred by their GP are seen in the outpatient clinic and, if their symptoms are suggestive of varicose vein disease, they are sent to have a venous duplex scan. This usually happens on a different day. Afterwards, they are seen back in the clinic (again on a different day) and, if the scan result suggests venous incompetence amenable to day case treatment, they are added to the waiting list. The eventual procedure takes place some time later (within 18 weeks from referral to treatment). After their procedure, they will be asked to fill a Picker patient experience questionnaire. On discharge, they will be given a diary card to fill for when they return to their normal activities and work. At 3 months post intervention, patients randomised to the normal care pathway will be sent the QoL questionnaires again and asked to fill the AVVQ, CIVIQ, EQ-5D and Picker patient experience questionnaires. As there will be an inherent delay in the NCP pathway we can not use the time from randomisation as many patients will not have received their interventional treatment by then.

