### **Secondary Outcome**

- Patient satisfaction with the service provided using the Picker patient experience questionnaire both post-operatively and at the 3 months follow-up (One Stop Vein Clinic versus Normal Care Pathway)
- Measure and compare the quality of life scores using EQ-5D, AVVQ and CIVIQ at 0 and 3 months in patients randomised to treatment in the One Stop Vein Clinic with patients randomised to the Normal Care Pathway
- Time from referral to treatment
- Assess the cost-effectiveness of the One Stop Vein clinic compared to the normal care pathway
- Record the time to return to normal activities and to work
- Assess the estimated societal costs

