## **STUDY DURATION & SAMPLE SIZE**

Following screening of their GP referral letter, patients with varicose vein disease will be invited to participate in the study. We estimate that 12-14 patients will be invited on a weekly basis to participate in the study following screening. Out of those, we are anticipating only 8 patients will agree to be randomised to the One Stop Vein Clinic or Normal Care Pathway. If the clinic is held weekly, we estimate recruiting 416 patients over the course of the year (8 patients X 52 weeks).

Statistical analysis suggests that the sample size of 208 patients per group would be able to power a potential phase 3 multicentre randomised controlled trial. Compared to a previous study conducted in our unit which involved 317 patients in total and looked at different quality of life scores and their responsiveness, the coefficient of variation (ratio of standard deviation to mean) was found to increase at the follow-up period and to vary among the different scores used. With a larger sample size as in this pilot study, this variability would be reduced and result in a smaller coefficient of variation when looking at the follow-up scores. Hopefully, this will enable us to identify the QoL score with the least variability and use it as the primary outcome measure in a future Phase 3 study. A primary outcome measure with little variability would provide us with enough information to estimate an adequate sample size for any future randomised controlled trials.

For example, with a sample size of 208 patients and coefficient of variation of 0.5, a 15% reduction in the geometric mean (a measure of central tendency, similar to median) would be required compared to 25% from the Shepherd et al. study. With power at 85%, this would allow us to determine an adequate sample size.

Participants will be followed-up post-procedure for 3 months, including for patients randomised to the Normal Care Pathway (with potentially longer waiting time from referral to treatment). This means that the study period will be about 18 months. With 3 months for study start-up and 3 months to write the study up, the study will last for 24 months.

Approximately 1,000 patients undergo varicose vein procedures at the Imperial College NHS Trust every year.

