#### **Estimated societal costs.**

Data will be collected on time off from work and carer's duties (child/relative/friend). Additionally, data on income, cost of attending clinic and impact on family and colleagues will be assessed to estimate the societal cost of the two pathways.

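### The patient diary supports return-to-work analysis only up to day 10 and cannot supply working days lost during recovery

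*Protocol*

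**What the plan says.** The Protocol's Secondary Outcome list includes: "Record the time to return to normal activities and to work". Both pathway descriptions hand out a card at discharge; for the normal care pathway, "they will be given a diary card to fill for when they return to their normal activities and work".

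Appendix 9 prints that card. Its instruction reads "Please indicate at what stage you were able to return to work and your normal daily activities", and the work item is headed "Day I returned to work (please tick one box)". There are 12 boxes: "Day of surgery", the day after, each day from 2 to 10, and finally ">10 days after surgery". No date, count of working days or employment status is requested.

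Under Estimated societal costs the Protocol says: "Data will be collected on time off from work and carer's duties". Appendix 3, the societal questionnaire, asks whether time off was needed to attend an appointment, whether it was a half or full day, and the hourly rate of pay. Appendix 4 has a free-text occupation field.

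**The concern.** The form itself limits the data. Coding and censoring rules can be left to a statistical analysis plan, but no plan can recover what the form never asked.

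Three things are missing:

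- **Duration beyond day 10.** A return on day 11 and one on day 60 produce the same tick, although patients are followed for 3 months.
- **Working days missed.** Elapsed days since surgery do not convert to working days without the weekday of treatment and the patient's work pattern.
- **Employment status.** A blank work answer may mean not employed, not yet returned, or not answered, so the denominator for return to work is unclear.

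At stake are the completeness of one secondary outcome and a likely input to another, the societal cost. Costing needs a mean, and a mean is what an open top category damages.

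**Working it through.** The Protocol gives no figure for return to work, so there is nothing to reproduce. Four checks follow; the first needs no assumption.

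**1. Is work lost in recovery collected elsewhere?** Appendix 3 covers attendance only (half or full day) and pay. Appendix 4 covers occupation only. The 3-month postal pack, as listed in both pathway descriptions, contains AVVQ, CIVIQ, EQ-5D and the Picker questionnaire. None gives the length of absence after treatment.

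**2. What does one tick mean in working days?** Assume a Monday-to-Friday worker who returns on a weekday. Count the weekdays strictly between surgery and return:

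| Box ticked | Working days missed, by surgery weekday |
|---|---|
| 3 days | 2 (Mon, Tue); 0 (Fri) |
| 4 days | 3 (Mon); 1 (Thu, Fri) |
| 10 days | 7 (Mon, Tue); 5 (Fri) |
| 0–2 and 5–9 days | one value per box, whatever the weekday |

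The ambiguity is at most 2 working days and affects three of the numbered boxes. Other work patterns would differ, and the card does not ask for the pattern.

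**3. What does the open box cost?** The share returning after day 10 is not in the documents. As an illustration, take lognormal return times cut to whole days, with assumed medians of 3 to 10 days and log-SD of 0.6 or 0.9. Compare the true mean of elapsed days with the mean after coding the open box as 11:

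| Median | log-SD | Share >10 | True mean | Coded mean | Shortfall |
|---|---|---|---|---|---|
| 3 | 0.6 | 1.5% | 3.09 | 3.05 | 0.04 |
| 3 | 0.9 | 7.5% | 4.00 | 3.53 | 0.47 |
| 5 | 0.6 | 9.5% | 5.49 | 5.15 | 0.34 |
| 5 | 0.9 | 19.1% | 7.01 | 5.37 | 1.64 |
| 7 | 0.6 | 22.6% | 7.88 | 6.79 | 1.09 |
| 7 | 0.9 | 30.7% | 9.99 | 6.66 | 3.33 |
| 10 | 0.6 | 43.7% | 11.47 | 8.47 | 3.00 |
| 10 | 0.9 | 45.8% | 14.50 | 7.96 | 6.54 |

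In every row fewer than half exceed day 10, so the median is unaffected. Only the mean suffers.

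**4. Could the weekday effect differ by arm?** Only if the One Stop clinic has a fixed weekday that differs from normal-pathway lists. The Protocol says no more than "If the clinic is held weekly, we estimate recruiting 416 patients". Suppose normal-pathway procedures are spread evenly over Monday to Friday.

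- If recovery takes 1 working day off, return falls on elapsed day 2, 2, 2, 4, 4 for Monday to Friday surgery. The mean is 14/5 = 2.8. A Friday clinic differs by 4.0 − 2.8 = +1.2 days and a Monday clinic by 2.0 − 2.8 = −0.8.
- If the patient is fit on elapsed day 2 and returns on the next weekday, the days are 2, 2, 2, 4, 3. The mean is 13/5 = 2.6. A Friday clinic differs by +0.4 and a Thursday clinic by +1.4.

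Size and sign depend on the assumed weekday, and the size also on the recovery model.

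**The case against.** A reader might go further and infer three things that the documents do not support.

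*The diary cannot validly measure return to work.* It can, within limits. A tick in the open box is a right-censored observation. Among identified workers, the proportions returned by each day up to 10 are valid, and so is the median if fewer than half exceed day 10. Elapsed days are a legitimate unit for time to return. Coding the open box as 11 is an illustration here, not a rule in the Protocol.

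*The comparison between arms is biased by weekday.* No treatment weekday is given for either arm, and they could coincide. The date of treatment must be known for the referral-to-treatment outcome, so weekday can be derived and adjusted for, although work pattern cannot. This remains a conditional risk.

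*The societal cost will be understated.* The Protocol does not say that the diary feeds that cost or how the cost is calculated. Appendix 3 is explicitly about attending appointments, which is where the pathways differ by design. The treatments are minimally invasive, under local anaesthetic with same-day discharge, and the same options are described for both arms, so late returns may be few and similar between arms.

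The employment gap is also partly covered. Occupation and the work and pay questions will identify some non-workers, and a completed activities answer beside a blank work answer shows that the card came back. These clues are not linked to the diary, however. Answering no to time off does not mean not employed, and a blank beside a completed activities answer may still mean not yet returned.

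What stands is that absence beyond day 10 and working days missed are on no printed form, and that employment status must be pieced together.

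**Conclusion.** The point holds in a limited form. The card supports a right-censored analysis of time to return up to day 10. It cannot give mean working days lost during recovery, and no other printed form fills that gap. A societal cost that includes time off work beyond attendance would need that figure. The missing employment option leaves the return-to-work denominator partly unclear.

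The size cannot be fixed from the documents. Under the assumed distributions the understatement of mean elapsed time runs from negligible (0.04 days) to 6.5 days, driven by the unknown share returning after day 10. The box-to-working-day ambiguity is at most 2 days for a Monday-to-Friday worker. Any difference between arms from clinic weekday is hypothetical.

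This is a cheap improvement to secondary outcomes. The primary QALY outcome is not touched. It is worth making because the data cannot be reconstructed later and the pilot is meant to inform a larger trial.

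**What to change.** Replace the tick boxes in Appendix 9 with five items: date of procedure; date normal activities were resumed; date of return to work; number of normal working days missed; and a box for not in paid work. Collect the card with the 3-month postal questionnaires so that later returns are captured, and add it to the listed contents of that pack in both pathway descriptions. Keep elapsed time for the return-to-activities and return-to-work outcome, and use working days missed for any productivity cost.

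The cost is a one-page form revision, slightly more writing for patients, and one more item in the 3-month mailing.
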